## 1 DOCUMENT HISTORY

Version	Issue Date	Protocol Amendment Number and Description of Change(s)
1.0	22 June 2021	NA
2.0	07 September 2023	
Amendment N. 1
 
Major/Substantial changes:
 
 
Sections 7 Protocol Synopsis and 12.1 Inclusion Criteria: Inclusion criterion #2 has been changed from “Primary CH diagnosis with elevated TSH and low T4...” to “Primary CH diagnosis with elevated TSH and low or normal FT4...”, in order to include not only subjects with severe disease, but also those with mild to moderate disease, and to account for the new AAP guidelines on screening and management of congenital hypothyroidism recommending diagnosis based on TSH and FT4 (Rose 2023). Inclusion criterion #2 has moreover been changed from “...Infants (aged 29 days to 277 days) previously diagnosed with primary CH and who are already on LT4 therapy for at least 4 weeks” to “...Infants (aged 29 days to 277 days) previously diagnosed with primary CH and who are already on LT4 therapy for at least 3 weeks”, to account for the recommended periodicity of therapy monitoring with one scheduled control usually falling at 3 to 4 weeks after the initiation of LT4 treatment (Rose 2023). Rationale on the choice of the inclusion criterion has been added in Section 11.2.
 
Sections 7 Protocol Synopsis and 12.2 Exclusion Criteria: Exclusion criterion #2 has been changed from “Low birth weight (LBW) and very low birth weight (VLBW) neonates (weight < 2.5 kg)” to “Low birth weight (LBW) or very low birth weight (VLBW) neonates (weight < 2.5 kg) or VLBW infants (weight < 1.5 kg)” in order to exclude from the study infants who were born VLBW. This population is indeed considered particularly fragile and at risk of death for the first year of life and this may jeopardize the participation in the study. Rationale on the choice of exclusion of VLBW subjects has been added in Section 11.2.
 

		
 
Sections 7 Protocol Synopsis and 12.2 Exclusion Criteria: Exclusion criterion #3 has been changed from “Neonates in neonatal intensive care units (NICU) or requiring admission to NICU or neonates/infants hospitalized or requiring hospitalization” to “Neonates in neonatal intensive care units (NICU) or requiring admission to NICU or neonates/infants hospitalized or requiring hospitalization or in fragile health conditions (e.g. with serious health problems or complications)”, fragile health conditions may jeopardize the participation in the study. Rationale on the choice of this exclusion criterion has been added in Section 11.2.
 
Sections 12.4 Screen Failures and 16.1 Screening/Inclusion (Randomization) – Visit 1 (Day -14 To 1): the re-screening of subjects will be allowed, if eligibility has changed, but re-screening may happen only once, upon re-consenting and upon assignment of a new Subject Number.
 
Sections 7 Protocol Synopsis, 15.1.1 Laboratory Parameters, 15.3.1 Dosing Evaluation and 16 Overall Study Schedule: the analysis of TT4 has been made optional, at the discretion of the Investigator, because the most recent AAP guidelines on medical management of congenital hypothyroidism (Rose 2023) recommend TSH and FT4 as the main parameters for laboratory monitoring of the LT4 treatment. Rationale has been included under section 11.2.
 
Sections 15.1.1 Laboratory Parameters, 16.2 Treatment Phase and Table 1 Schedule of Evaluations: the window for blood samples collection for serum FT4, TT4 and TSH monitoring, as well as for the conduct of all visit procedures, has been extended from 0-4 days to 0-7 days within the allowed visit time frame, to allow more flexibility to subjects and sites.
 
Sections 15.1.1 Laboratory Parameters and 22.1 Biological Samples have been updated in order to allow the possibility to use more than one single laboratory at each site, as well as to have blood drawn as per SOC at a laboratory patient service center, so to decrease the discomfort for the subjects related to having all blood draws at the clinical site, particularly when living distant from the site. In order to reduce variability, the request to use the same lab for the same subject has been added. Also, the timing for samples analysis has been extended from 24 to 24-72 hours.
 

--	--	---

		
 
• Section 16.2.3 Visit 2 (Study Day 8-15, i.e. 7-14 Days After Treatment Start) and Table 1 Schedule of Evaluations: blood draw at Visit 2 (7-14 days after treatment start) has been changed from mandatory to optional, at the discretion of the Investigator, for infants already on LT4, because this early control is not SOC for infants who are stable on LT4 and it would cause unnecessary discomfort to them.
 
• Section 16.2.16 Unscheduled Visits: since unscheduled visits are frequently done to the sole purpose of drug dispensing, AEs and concomitant medications recording will not be mandatory in that case.
 
• Section 16.1 Screening/Inclusion (Randomization) – Visit 1 (Day -14 to 1) and Table 1 Schedule of Evaluations: for infants presenting at Visit 1 with routine laboratory results already available, the acceptability of these results has been extended from 2 weeks to <28 days, in order to reduce the discomfort of additional blood sampling in a short period of time. Though, the possibility to repeat blood tests at V1, if needed as per Investigator's judgement, has been maintained. In addition, it has been clarified that, where acceptable routine lab results are available, these will have to be recorded in the CRF.
 
 
Minor changes/Clarifications:
 
 
• Table 1 Schedule of Evaluations and Section 16 Overall Study Schedule have been updated to correct a few discrepancies in Study Day numbers between Table 1 and Section 16, and to provide additional clarifications, without substantial changes in the procedures other than those described above.
 
• Table 1 Schedule of Evaluations has been updated for release of CareCAT during the third week of treatment on days 15-21 instead of days 15-22.
 
• Table 2 Outline of Visit Schedule Based on Age has been updated in order to correct few discrepancies in Study Day numbers between Table 2 and the text in Section 16 Overall Study Schedule, without substantial changes in the procedures other than those described above.
 
• Background information provided in Sections 8 Introduction, 11 Trial Design and 13 Treatments has been reviewed in light of the new guidelines on the screening and management of
 

--	--	---

		
congenital hypothyroidism by the AAP (Rose 2023), with no substantial impact on the study plan and procedures.
 
 
• The literature overview in Section 8.1 Background has been updated with the most recent papers published on the use of LT4 oral solutions in congenital hypothyroidism, with no impact on the risk/benefit profile of the study.
 
• Sections 11.2 Scientific Rationale for Study Design has been updated to clarify reliance on SOC for CH diagnosis, the definition of “elevated”, “low” and “normal” TSH and FT4 results and the fact that local laboratory normal ranges are not the only reference ranges that the Investigator can take into account in their evaluation of hormonal results, but medical guidances, as well as relevant literature and manuals may also be taken in consideration. This is related to the fact that local laboratories normal ranges are highly variable and not always age-specific in terms of days from birth. This change is not intended to modify the study procedures, but to provide more clarity on the topic. In addition, the rationale for the changes in inclusion/exclusion criteria and assessments has been added.
 
• In Sections 7 Protocol Synopsis and 12.2 Exclusion Criteria, Exclusion criterion #4 has been re-worded for uniformity of wording with other criteria. In addition, the clarification has been provided that the wording “neonates” and “infants” are to be intended as defined in inclusion criterion #2. These modifications don’t change the meaning of the criteria, but are intended to clarify it.
 
• In Sections 7 Protocol Synopsis and 13.1 Study Drug (IP), the strength of 13 mcg has been added among the strengths supplied in order to cover potential needs of fine dose adaptations. Supply of additional strengths among those authorized for Tirosint-SOL was already foreseen by the protocol.
 
• Section 12.5 Strategies for Recruitment and Retention: the aim of external recruitment efforts has been better specified and the possibility of dissemination of information to the public has been added.
 
• Section 13.2.1 Packaging and Labelling has been corrected to reflect actual labelling information.
 

--	--	--

		
 
• In Section 15 Study Assessments and Procedures it has been clarified when clinically significant abnormalities detected at study assessments are to be recorded as medical history or AEs and when not.
 
• Section 15.1.2 Parents' Satisfaction Questionnaire has been updated to ask Investigators to verify completion of the questionnaire and, if not completed, ask parents to complete it on site during the visits, in order to improve compliance with this assessment.
 
• Section 16.1 Screening/Inclusion (Randomization) – Visit 1 (Day -14 to 1) and Table 1 Schedule of Evaluations: the definition of “first day of study drug administration” for subjects who were already on tablets and remain on tablets during the study has been clarified.
 
• Sections 16.2.1 Normalization Phase, 16.2.2 Long-Term Follow-Up Phase and Table 1 Schedule of Evaluations: it has been clarified that if a Follow-Up Visit (Type 1 or 2) overlaps with a planned visit, it is possible to perform only the planned visit, consistently with SOC.
 
• Section 16.2.2 and Table 1 Schedule of Evaluations: Follow-up Type 2 visits have been made optional, at Investigator's judgement, in case an abnormal T4 or TSH are found, for consistency with the SOC (they remain mandatory in case of dose adjustment).
 
• Sections 7.2 Organizational and Administrative Structure and 17.5 Reporting and 17.7 Follow-up: a new email address of Drug Safety Unit for SAEs notification has been added, the list of persons to be informed has been updated, and some instructions regarding the information to be provided by the Investigator have been added.
 
• Section 18.1 Data Collection: the latest definition of ALCOA has been added.
 
• Sections 7 Protocol Synopsis and 19.3.2 Efficacy Outcomes: statistical analysis of TT4 will be conducted only if an adequate number of observations will be available, since the evaluation of this laboratory parameter at each visit will be optional. Moreover, the statistical analysis for events of TSH values above 4.5 mIU/L and FT4 values below the middle of the laboratory normal range has been modified from analysis
 

--	--	--

		
of variances into logistic models because it is deemed more appropriate for the data type.
 
 
• Section 20.2 Quality Control And Quality Assurance: the monitoring of Quality Tolerance Limits during the course of the study has been added.
 
• Minor inconsistencies/discrepancies have been corrected throughout the text.
 
 
Administrative changes:
 
 
• Cover page: Clinicaltrial.gov number has been added
 
• Section 3 List of Abbreviations: the list has been updated
 
• Cover page and Section 7.2 Organizational and Administrative Structure: Sponsor's Legal Address has been updated.
 
• Cover page and Section 7.2 Organizational and Administrative Structure: Sponsor's Study Manager's information have been updated.
 
• Section 7.2 Organizational and Administrative Structure: Sponsor's United States Representative has been deleted.
 
• Section 7 Protocol Synopsis: Due to delays in recruitment, overall study duration has been extended from 22 to 39 months (enrolment time from 10 to 26 months) and the estimated date for last patient completed from July 2023 to December 2024.
 
• Section 19.3.1 General Statistical Methods: SAS version in use for the statistical analysis has been updated.
 

--	--	--

## **2 STATEMENT OF COMPLIANCE**

The trial will be carried out in accordance with the International Conference on Harmonization Good Clinical Practice (ICH GCP) and the United States (US) Code of Federal Regulations (CFR) 45 CFR Part 46, 21 CFR Part 50, 21 CFR Part 56, 21 CFR Part 312, 21 CFR Part 11, and/or 21 CFR Part 812.

The protocol, informed consent form(s), recruitment materials, and all subject materials will be submitted to the Institutional Review Board (IRB) for review and approval. Approval of both the protocol and the consent form(s) will be obtained before any subject is enrolled. Any major amendment to the protocol will require review and approval by the IRB before the changes are implemented. In addition, all changes to the consent form will be IRB-approved; a determination will be made regarding whether a new consent needs to be obtained from subject who already provided consent using a previously approved consent form.

### 3 LIST OF ABBREVIATIONS

AAP	American Academy of Pediatrics
ADR	Adverse Drug Reaction
AE	Adverse Event
ALCOA	Attributable, Legible, Contemporaneous, Original and Accurate
ATC	Anatomical Therapeutic Chemical
BW	Body Weight
CareCAT	Caregiver Administered Children's Acceptance Tool
CFR	Code of Federal Regulations
CH	Congenital Hypothyroidism
CMP	Clinical Monitoring Plan
CRO	Clinical Research Organization
CSR	Clinical Study Report
CTA	Clinical Trial Agreement
DMC	Data Monitoring Committee
DMP	Data Management Plan
DSU	Drug Safety Unit
eCRF	Electronic Case Report Forms
EDC	Electronic Data Capture
EOS	End of Study
EU	European Union
FAS	Full Analysis Set
FDA	Food and Drug Administration
FPFV	First Patient First Visit
FT4	Free Thyroxine
FU	Follow-Up
GCP	Good Clinical Practice
GI	Gastrointestinal
HR	Heart Rate
ICF	Informed Consent Form
ICH	International Conference of Harmonization
ID	Subject Identification
IND	Investigational New Drug
IP	Investigational Product (Study Drug)
IQ	Intellectual Quotient
IRB	Institutional Review Board
ISF	Investigator Site File
IWRS	Integrated Web Response System

LBW	Low Birth Weight
LPLV	Last Patient Last Visit
LT4	Levothyroxine
LOCF	Last Observation Carried Forward
MedDRA	Medical Dictionary for Regulatory Activities
NICU	Neonatal Intensive Care Unit
PI	Principle Investigator
PPI	Proton Pump Inhibitors
PPS	Per Protocol Set
PT	Preferred Term
PTAE	Pre-Treatment Adverse Event
SAE	Serious Adverse Event
SAF	Safety Analysis Set
SAP	Statistical Analysis Plan
SAR	Serious Adverse Reaction
SOC	Standard of Care
SOC (MedDRA)	System Organ Class
SOE	Schedule of Evaluations
SOP	Standard Operating Procedure
SUSAR	Suspected Unexpected Serious Adverse Reaction
T3	Triiodothyronine
T4	Thyroxine
TT4	Total Thyroxine
TFT	Thyroid Function Test
TH	Thyroid Hormone
TM	Telemedicine
TSH	Thyroid Stimulating Hormone
US	United States
USPI	United States Prescribing Information
VLBW	Very Low Birth Weight
WHO-DRL	World Health Organization – Drug Reference List

## 7 PROTOCOL SYNOPSIS

Title:	A Randomized Comparative Study Between Liquid (Tirosint®-SOL) and Tablet Formulations of Levothyroxine in Neonates and Infants with Congenital Hypothyroidism (CH)
Protocol:	20US-T414
Phase:	IV
Study Site(s):	Up to 20 sites in the United States
Study Objective:	
The objective of this study is to gather information on the use of Tirosint®-SOL oral solution as thyroid hormone (TH) replacement therapy in neonates and infants with CH compared to the conventional treatment with crushed levothyroxine sodium (LT4) tablets. Specifically of interest is comparing the ease of administration and acceptability, the thyroid function tests (TFTs) profile, the LT4 dose required to maintain thyroid stimulating hormone (TSH) in the target range, as well as the growth pattern between the treatment groups.

Study Design:	
This is a multi-center, prospective, parallel-group, open-label, randomized clinical study in one hundred and twenty-six (126) subjects (neonates and infants diagnosed with CH).
 
Subjects will be randomized in a 2:1 ratio to Treatment (Tirosint®-SOL) or Control (levothyroxine sodium crushed tablets).
 
Newly diagnosed neonates will be randomly assigned to start therapy with LT4 at the initial dose recommended by the Standard of Care (SOC).
 
Infants already on LT4 therapy will continue at the same daily dose within the randomly assigned treatment group (dose adjustments are allowed, if needed based on laboratory parameters and clinical response).
 
Once enrolled, subjects will be treated and followed for 12 months (<math>\pm 1.5</math> months), participating in 7-8 study visits, consisting of 6-7 in-clinic and 1-2 (or more if follow-up visits are required) telemedicine (TM) visits. The total number of visits depends on the age at inclusion as reported in Table 2. In-clinic visits are performed between 3-4 weeks after randomization, when the subject is 4, 6, and 9 months of age, and then every 3 months as required depending on the age at the inclusion. TM visits will be performed between 1-2 weeks after randomization, when the subject is 2 months of age, if

	applicable, and any time an additional follow-up is required for TSH and thyroxine (T4) monitoring.
Study Duration:	Planned treatment duration per subject: ~12 months Overall study duration: ~39 months (26 months to enroll all subjects).
Treatment:	
Study Drug: Tirosint®-SOL (levothyroxine sodium) oral solution (IBSA Pharma Inc.) at the following strengths: 13, 25, 37.5, 44, 50, 62.5, 75, 88, 100 mcg.
 
Control: Currently prescribed crushed LT4 tablets or, in case of newly diagnosed neonates, crushed LT4 tablets as determined by SOC.
 
Dose: The dose will be based on body weight (BW) and age of each subject, and adjusted based on clinical response and laboratory parameters according to SOC and Investigator's judgement. The general aim of therapy should be to normalize the serum TSH level (it is suggested to target the mid- to lower half of the normal range whenever appropriate), and to increase the serum T4 into the upper half of the normal range.
 
Mode of administration: Both products will be used according to the United States Prescribing Information (USPI) and SOC.

Study Population:	
126 subjects meeting the following criteria will be enrolled.
 
Inclusion Criteria:
 
 
1. Male and female subjects aged 0 to 9 months (277 days) at Inclusion;
 
2. Primary CH diagnosis with elevated TSH and low or normal FT4, requiring treatment with LT4, under either of the following conditions: 
 
• Neonates (aged 0 to 28 days) newly diagnosed with primary CH and needing to initiate LT4 therapy, or
 
• Infants (aged 29 days to 277 days) previously diagnosed with primary CH and who are already on LT4 therapy for at least 3 weeks;
 
 
 
3. Parent or legal guardian of the subject provides voluntary written and informed consent prior to initiation of any study procedures; and
 
4. Parent or legal guardian of the subject is willing and able to comply with scheduled visits and all study activities.
 
 
Exclusion Criteria:

	
 
1. Preterm neonates with a gestational age < 37 weeks;
 
2. Low birth weight (LBW) or very low birth weight (VLBW) neonates (weight < 2.5 kg) or VLBW infants (weight < 1.5 kg);
 
3. Neonates in neonatal intensive care units (NICU) or requiring admission to NICU or neonates/infants hospitalized or requiring hospitalization or in fragile health conditions (e.g. with serious health problems or complications);
 
4. Neonates with CH diagnosis > 4 weeks after delivery;
 
5. Diagnosis of primary gastrointestinal (GI) disease: 
 
a. Gastroesophageal reflux requiring medical therapy (beyond thickening of formula or position);
 
b. Anatomic defects (e.g. intestinal atresia, malrotation, tracheoesophageal fistula, pyloric stenosis, Hirschsprung's disease, gastroschisis);
 
c. Dietary allergy (e.g. cow's milk protein allergy);
 
d. Malabsorption related to cystic fibrosis, celiac disease and others;
 
e. Necrotizing enterocolitis requiring surgical resection;
 
 
 
6. Known or suspected adrenal insufficiency (e.g. congenital adrenal hyperplasia, hypopituitarism);
 
7. Diagnosis of congenital cardiac disease, cardiac insufficiency or risk for cardiac failure;
 
8. Diagnosis of chromosomopathy;
 
9. Diagnosis of central hypothyroidism;
 
10. Hypersensitivity to glycerol;
 
11. Concomitant anticonvulsant medications, liothyronine, combination of LT4 and liothyronine, thyroid extracts and/or chronic or long-term use of systemic glucocorticoids (see Section 13.2.5 for details);
 
12. History of nonadherence with medication or medical visit schedule; or
 
13. Any condition for which, participation would not be in the best interest of the subject or that could limit protocol specified assessments, according to the Investigator.
 

Study Assessments:	
Efficacy Assessments:
 
 
• Laboratory parameters (TSH, free thyroxine [FT4], and optional total thyroxine [TT4]);
 
• Parents' Satisfaction Questionnaire; and
 

	
 
Caregiver Administered Children's Acceptance Tool (CareCAT).
 
 
Safety Assessments:
 
 
Physical examination and vital signs;
 
Growth assessments (length, BW, head circumference);
 
Hypo- and hyper- thyroidism signs and symptoms; and
 
Adverse events (AEs).
 
 
Other Assessments:
 
 
Dosing evaluation;
 
Treatment compliance; and
 
Nutritional intake.
 

Main Outcomes:	
 
Daily LT4 dose/kg required to maintain TSH in target range;
 
Frequency of dose adjustments;
 
Overall TSH, FT4 and, where available, TT4 values;
 
The number of events (TSH values) above 4.5 mU/L for TSH;
 
The number of events (FT4 values) below the middle of the laboratory normal range for FT4 for age;
 
Presence of signs and symptoms of hypo- and hyper-thyroidism;
 
Acceptance of medications evaluated by means of the CareCAT;
 
Ease of administration evaluated by means of Parents' Satisfaction Questionnaire; and
 
Growth patterns: 
 
Length;
 
BW;
 
Head circumference.
 
 
 

Exploratory Outcomes:	
For newly diagnosed neonates:
 
 
Time to normalize TSH into reference range; and
 
Time to normalize FT4 into the upper half of the laboratory normal FT4 range for age.
 

Statistical Methods:	
Sample size:
 
Subjects will be randomized in a 2:1 ratio to Treatment (Tirosint®-SOL) or Control (conventional therapy with levothyroxine sodium crushed tablets). Considering a mean value of 6 mcg/kg/day of LT4 dose at 12 months of age and a standard deviation of 2 mcg/kg, a sample size of 102 neonates and infants (68 Treatment and 34 Control)

will have 80% power to detect a difference of 20% in the LT4 dose between the groups using an independent t-test with a 0.050 two-tailed significance level. To account for a drop-out rate of maximum 20%, 126 neonates and infants will be enrolled in the study (84 Treatment and 42 Control).

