Tirosint®-SOL is bioequivalent to Tirosint (levothyroxine sodium) capsules when administered in healthy adult volunteers. In addition, administration of Tirosint®-SOL upon dilution in water is bioequivalent to administration of Tirosint®-SOL directly into the mouth in healthy adult volunteers ([Tanguay 2019](#)).

Although use of LT4 oral solutions in the US is limited, use in other countries indicates that they are safe and effective in the treatment of CH and may present some advantages in terms of ease of administration. The relevant clinical experience is detailed below.

In a retrospective study of 78 newborns with CH taking liquid LT4, it was demonstrated that normalization of serum TH concentration was obtained within 7-10 days of administration in 87% of group A (liquid) subjects and 82% of group B (tablet) subjects, at doses ranging between 10

and 15 µg/kg/day. Group A subjects had significantly lower TSH values compared with those of group B at 7-10 days ( $p = 0.05$ ) and 6-8 months ( $p = 0.043$ ) of treatment, despite similar L-T4 dose and FT4 concentration. Mean Developmental Quotient scores were within normal range in all subjects. When comparing the effects of liquid and tablet formulation in the treatment of infants with CH, the study confirmed the efficacy and safety of both formulations using dosages recommended by CH guidelines ([Peroni 2013](#)).

In a prospective study in 42 newborns with CH, there were significantly more subjects with suppressed TSH concentrations in group 1 (liquid) than in group 2 (tablet). In the moderate/mild form of CH, the subjects of group 1 and group 2 showed median values of TSH, FT3, and FT4 that were not significantly different. No clinical or electrocardiographic signs of heart disease were found. There were no significant differences in the developmental quotient between the groups. The authors concluded that data indicated non-complete bioequivalence between the liquid and tablet formulations, especially in infants with severe CH ([Cassio 2013](#)).

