### 13.1.2 DOSAGE AND ADMINISTRATION

Both products will be used and dosed according to the USPI and SOC.

The dose administered will be based on the subject's BW and age, and adjusted based on clinical response and laboratory parameters according to SOC and PI's judgement.

These procedures are informed by the main treatment guidelines, as well as in the USPI of Tirosint®-SOL and LT4 tablets ([Synthroid USPI](#), [Tirosint®-SOL USPI](#)), as described in **Section 11.3**.

**Further to these general principles, Investigators are required to follow the SOC in order to define the correct dose and treatment goal for each subject.**

Initial Dosing in newly diagnosed neonates:

- Replacement therapy with LT4 should be started as promptly as possible upon diagnosis of CH.
- **Inclusion in the study must not delay the start of LT4 treatment.**
- Initial neonate LT4 dose should be between 10-15 mcg/kg;
- The initial dose should take into account the severity of the disease; and
- The goal of therapy should be to normalize FT4 into the upper half of the reference range and TSH within the reference range (it is suggested, within the mid- to lower half of the reference range whenever appropriate).

Initial Dosing in infants already under LT4 therapy:

- Subjects will be switched directly from crushed LT4 tablets to Tirosint®-Sol or continue on crushed LT4 tablets, with **no treatment interruption**.
- Same dose used before screening should be maintained, if replacement is adequate at screening/inclusion; or
- Dose should be adjusted at inclusion, if needed based on laboratory parameters and clinical response.

Dosing throughout study in neonates and infants:

- Dose adjustments can be done whenever required throughout the study and will be defined based on the evaluation of T4 and TSH values and clinical response according to SOC; and
- Therapy should aim to maintain serum TSH concentration in the age specific laboratory reference range (it is suggested, to target the mid- to lower half of the reference range whenever appropriate) and serum T4 concentration in the upper half of the age specific laboratory reference range.

If dose fine tuning is required, which cannot be obtained with the available strengths, alternating two strengths over the course of the week may be allowed. All dosing schemes must be documented in the EDC.

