### **19.1 SAMPLE SIZE**

Subjects will be randomized in a 2:1 ratio to Treatment (Tirosint®-SOL) or Control (conventional therapy with LT4 crushed tablets). Considering a mean value of 6 mcg/kg/day of LT4 dose at 12

months of age (**Table 3**) and a standard deviation of 2 mcg/kg, a sample size of 102 neonates and infants (68 Treatment and 34 Control) will have 80% power to detect a difference of 20% in the LT4 dose between the groups using an independent t-test with a 0.050 two-tailed significance level. To account for a drop-out rate of maximum 20%, 126 neonates and infants will be enrolled in the study (84 Treatment and 42 Control) ([Peroni 2013](#))

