9.3 DEMOGRAPHIC AND SCREENING/BASELINE CHARACTERISTICS

Descriptive statistics of baseline characteristics will be presented for the Full Analysis Set (FAS).

Subjects baseline characteristics will include:

- Demographic data: age at screening, age at randomization, age class (infant or neonates), gestational age, weight at birth, sex, race, ethnicity, length at screening, weight at screening, BMI at screening, head circumference at screening, TSH (mIU/L) and T-4 FREE (pmol/L) levels at CH diagnosis.
- LT4 dose: LT4 dose (mcg/kg/day) at screening (for infants only)
- Hormonal status: TSH (mIU/L) and T-4 FREE (pmol/L) levels at screening (for infants only).
- Vital signs: pulse and temperature at screening.
- Physical examination: abnormal body systems at screening.
- Signs and symptoms of hypo and hyper thyroidism: category (hypothyroidism or hyperthyroidism) and sign or symptom at screening.
- Nutritional intake: breast milk, cow's milk, formula milk, baby food or adult-like food at screening.
- Medical History: those will be summarized by System Organ Class (SOC) and Preferred Term (PT).
- Previous Medications: All previous medications will be summarized by Anatomical Therapeutic Chemical (ATC) level 2 and preferred drug name.

Age at screening, age at randomization, gestational age, weight at birth, length at screening, weight at screening, head circumference at screening, TSH (mIU/L) and T-4 FREE (pmol/L) levels at CH diagnosis, TSH (mIU/L) and T-4 FREE (pmol/L) levels at screening (for infants

only), and LT4 dose (mcg/kg/day) at screening (for infants only) differences between treatment groups will be evaluated using Wilcoxon test.

Sex, ethnicity and race will be compared between treatment groups at each visit using a Chi-squared test or, when the expected values in any of the cells of a contingency table are below 5 or the total number of observations is less than 20, Fisher exact test as appropriate.

The demographic data analysis will be repeated stratified on neonates and infants.

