9.4.1 Primary efficacy analysis

LT4 dose/kg

The LT4 dose/kg will be calculated based on the daily LT4 dose used in the time period preceding the visit and the body weight measured during the visit. When dosing schedules alternating strengths over the course of the week are used, the daily dose will be calculated as the average daily dose on a weekly basis.

The LT4 dose/kg required to maintain TSH in target range will be analyzed at 12 months of age visit (V8) and when the subject is 2, 4, 6, 9, 15, 18 and 21 months of age (V4, V5, V6, V7, V9, V10, V11) by means of analysis of covariance (mixed model), including treatment group, age at randomization and interactions between visit and treatment group as covariates. Treatment effect at each visit will be estimated.

Normal distribution for LT4 dose/kg will be tested with Shapiro Wilks, if data result not to be distributed as a normal distribution a log transformation will be applied.

The mixed model will be adjusted with Kenward-Roger method and the unconstructed covariance matrix will be used as first choice (other matrixes will be considered if there will be convergence problems).

Summary descriptive statistics will be provided for LT4 dose/kg and results at each visit will be compared between treatment groups by Wilcoxon Mann-Whitney test. This analysis will also be repeated stratified on neonates and infants.

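### The dose/kg model leaves out disease severity at diagnosis, which is already recorded, so a chance severity imbalance between two small arms can be mistaken for a formulation difference

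*Protocol*

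**What the plan says.** Inclusion criterion 2 (Protocol 7 and 12.1) admits children with "Primary CH diagnosis with elevated TSH and low or normal FT4, requiring treatment with LT4". The document history gives the reason for the wording: "in order to include not only subjects with severe disease, but also those with mild to moderate disease".

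Protocol 13.1.2, on initial dosing in newly diagnosed neonates, says: "The initial dose should take into account the severity of the disease". Sections 8.1 and 11.3 report guideline starting doses that also depend on severity.

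At Visit 1 (Protocol 16.1) the site records TSH, FT4 and/or TT4 from the original diagnosis. SAP 9.3 lists "TSH (mIU/L) and T-4 FREE (pmol/L) levels at CH diagnosis" among the baseline characteristics and compares them between arms with a Wilcoxon test.

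Randomisation is stratified by site and by neonate/infant group, not by severity (SAP 3.3). SAP 9.4.1 models dose/kg "including treatment group, age at randomization and interactions between visit and treatment group as covariates". SAP 3.4 removes the neonate/infant and center terms. Protocol 19.3.9 leaves additional covariance analyses to the SAP, which defines none for severity.

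The TSH and FT4 models (SAP 9.4.2) add a basal value, defined in SAP 4.1 as the last measurement before treatment start.

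**The concern.** Severity at diagnosis is a plausible determinant of how much LT4 a child needs. It precedes randomisation, so adjusting for it is legitimate, and it is already in the baseline data. Leaving it out has two costs. Any variation in dose/kg that severity explains stays in the residual and widens the interval for the formulation contrast. And if the arms happen to differ in severity, that difference passes into the dose/kg contrast.

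The only between-arm use of the diagnostic values is a baseline significance test. In a randomised trial such a test corrects nothing, and at this size it has little power to flag an imbalance that matters.

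**Working it through.** **Inputs from the documents.** Mean dose 6 and SD 2 mcg/kg/day at 12 months of age; a 20% difference, so 0.20 × 6 = 1.2 mcg/kg/day; two-sided 5% t-test; 68 v 34 evaluable (Protocol 19.1, SAP 3.2). 31 children randomised (SAP 3). 4 neonates, 3 v 1 (SAP 3.4), hence 31 − 4 = 27 infants already on LT4.

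**Assumptions.** Arms of 21 v 10: the overall split is not stated and this follows from 2:1. R² between diagnostic severity and dose/kg of 0.1 to 0.3: the documents give no figure. The calculation is for one visit and ignores age at randomization and repeated measures.

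**The plan's own figure.** Protocol 19.1 states that the planned sample "will have 80% power to detect a difference of 20% in the LT4 dose between the groups". Noncentral-t power at 68 v 34 with 1.2/2 = 0.6 SD is 80.8%, and at 66 v 33 it is 79.6%. The 102 reproduces.

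**Unadjusted analysis at 21 v 10.** SE = 2 × √(1/21 + 1/10) = 2 × 0.384 = 0.768 mcg/kg. Power for 1.2 is 32.7%.

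**Adjusted for one covariate.** SE = 0.768 × √(1 − R²) × √(1 + 1/27), with 28 residual degrees of freedom instead of 29. The last factor is the average variance cost of random covariate imbalance, 1 + 1/(N − 4) with N = 31.

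| R² | SE ratio to unadjusted | SE (mcg/kg) | Power for 1.2 |
|---|---|---|---|
| 0 (uninformative) | 1.018 | 0.783 | 31.6% |
| 0.1 | 0.966 | 0.742 | 34.5% |
| 0.2 | 0.911 | 0.700 | 38.1% |
| 0.3 | 0.852 | 0.655 | 42.5% |

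So the SE falls about 3% to 15%, and an uninformative covariate costs 32.7 − 31.6 = 1.1 points of power. Break-even is near R² = 0.04.

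**Effect of a chance imbalance.** The between-arm difference in a standardised severity score has SD √(1/21 + 1/10) = 0.384; the chance that it exceeds 0.5 SD in either direction is 19%. An imbalance of one standard error shifts the unadjusted dose contrast by √R² × 2 × 0.384:

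- R² 0.1: 0.24 mcg/kg (20% of 1.2)
- R² 0.2: 0.34 mcg/kg (29%)
- R² 0.3: 0.42 mcg/kg (35%)

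**Type I error.** In a 100,000-run simulation of the unadjusted t-test, overall type I error was 4.9% to 5.0%. Given an imbalance of at least one standard error it was 6.4% at a correlation of 0.3 (R² 0.09) and 9.0% at 0.5 (R² 0.25).

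**Cost of missing covariate values.** If three children dropped out of the adjusted model (say 19 v 9), power at R² 0.1 would be about 31%, below the unadjusted 32.7%. The handling of missing values therefore decides whether adjustment helps.

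**The case against.** A good deal of the opposing case stands.

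- **The error rate is not inflated.** A reader might infer that omitting severity makes the comparison invalid, or that an imbalance will be reported as a formulation effect. The documents do not support that. Randomisation keeps the overall error at 5%, the baseline table would show the imbalance, and SAP 3.4 and 9.4 declare all efficacy analyses exploratory.
- **The severity-dose link is written for starting doses.** Only 4 of the 31 children were neonates starting therapy. No passage links diagnostic severity to dose/kg at 12 months, and Table 3 ties dose to age and weight. The R² range is therefore an assumption.
- **The enrolled range may be narrower than the criterion suggests.** Normal FT4 was admitted only from version 2.0 (7 September 2023), and screening closed on 31 March 2024. How many children entered under the wider rule is not stated.
- **One cited study is about something else.** Its conclusion, "data indicated non-complete bioequivalence between the liquid and tablet formulations, especially in infants with severe CH", describes effect modification, which a main-effect covariate does not address. It is no argument for this adjustment.
- **Extending the point to TSH and FT4 is tempting but unsupported.** For the 27 infants the basal value is an on-treatment measurement and does not capture severity at diagnosis. But these outcomes are titrated toward a reference range, and nothing in the documents lets a gain be estimated.
- **The covariate is imperfect.** Values come from different laboratories, may be per unit of blood or of serum, and FT4 may be absent.

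What does not fall is the core: the dose/kg model contains no measure of severity, although one is recorded before randomisation.

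**Conclusion.** The point holds for dose/kg, as a modest and inexpensive improvement. The defect lies in the SAP 9.4.1 model, not in the inclusion criterion. Under the stated assumptions the likely gain runs from about 2 points of power (R² 0.1) to about 10 (R² 0.3), with protection against a conditional shift of 20% to 35% of the difference the trial was sized for. The possible loss is about 1 point, provided that no child is dropped for a missing covariate. Power stays far below 80% either way, so the value lies in the estimate and its interval rather than in the test. This supports an added supportive model, not replacement of the planned one.

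**What to change.** 1. In SAP 9.4.1 add one supportive dose/kg model: the current terms plus a single continuous severity covariate from the confirmatory serum sample at diagnosis, on a common unit scale. Report it beside the current model.
2. Name the covariate now, either FT4 or log TSH at diagnosis. Choose on completeness alone, without reference to treatment arm or outcome, and leave no switch to be decided later.
3. State a rule that keeps children whose covariate is missing, for example single mean imputation of the baseline covariate. This must be written as an exception to SAP 8, which replaces no missing values.
4. In SAP 9.3 keep the descriptive table of diagnostic TSH and FT4 and drop the between-arm Wilcoxon test of these two values.
5. List the change in SAP 3.4, as a covariance analysis of the kind Protocol 19.3.9 provides for.

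The cost is SAP wording, one model and one degree of freedom; no new data collection is needed. Between-laboratory noise will weaken the adjustment, some diagnostic values may be missing, and the results remain exploratory.
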